5.7.3.2 Pregnancy Testing

Female subjects of childbearing potential will be tested for serum β -human chorionic gonadotropin (hCG) at pretrial, for urine and/or serum β -human chorionic gonadotropin (hCG) predose and at the last trial visit. In the case of a positive or borderline serum β -hCG pregnancy test at the pretrial visit, the subject must not enter the trial; in the case of a positive

or borderline serum β -hCG pregnancy test during the trial, the pregnancy test should be repeated and confirmed positive. If the pregnancy has been confirmed the subject must be discontinued from the trial immediately and the pregnancy must be reported the Sponsor as outlined in Section 7.2.2.

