1.0 TRIAL SUMMARY

Abbreviated Title	MK-8504 Single Dose Study in HIV-1 Infected Patients
Sponsor Product Identifiers	MK-8504
Trial Phase	Phase Ib
Clinical Indication	Treatment of HIV-1 Infection
Trial Type	Interventional
Type of control	No treatment control
Route of administration	Oral
Trial Blinding	Unblinded Open-label
Treatment Groups	Up to four panels (Panel A, B, C and D) of 6 subjects each will receive a single dose of MK-8504.
Number of trial subjects	Approximately 18- 24 subjects will be enrolled.
Estimated duration of trial	The Sponsor estimates that the trial will require approximately 7 months from the time the first subject signs the informed consent until the last subject's last study-related phone call or visit.
Duration of Participation	Each subject will participate in the trial for approximately seven weeks from the time the subject signs the Informed Consent Form (ICF) through the final contact. After a screening phase of approximately four weeks, each subject will be receiving assigned treatment for one day. After the end of treatment each subject will be followed for 25 days, or longer if ART is not initiated.

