5.8 Subject Withdrawal/Discontinuation Criteria

5.8.1 Discontinuation of Treatment

Discontinuation of treatment does not represent withdrawal from the trial.

As certain data on clinical events beyond treatment discontinuation may be important to the study, they must be collected through the subject's last scheduled follow-up, even if the subject has discontinued treatment. Therefore, all subjects who discontinue trial treatment prior to completion of the treatment period will still continue to participate in the trial as specified in Section 6.0 - Trial Flow Chart and Section 7.1.4.1 – Withdrawal/Discontinuation, or if available, Protocol Clarification Letter.

Subjects may discontinue treatment at any time for any reason or be dropped from treatment at the discretion of the investigator should any untoward effect occur. In addition, a subject may be discontinued from treatment by the investigator or the Sponsor if treatment is inappropriate, the trial plan is violated, or for administrative and/or other safety reasons. Specific details regarding procedures to be performed at treatment discontinuation are provided in Section 7.1.4 – Other Procedures.

A subject must be discontinued from treatment but continue to be monitored in the trial for any of the following reasons:

- The subject or subject's legally acceptable representative requests to discontinue treatment.
- The subject has a medical condition or personal circumstance which, in the opinion of the investigator and/or Sponsor, placed the subject at unnecessary risk from continued administration of study drug.
- The subject has a confirmed positive serum pregnancy test.
- The subject has a positive urine drug screen (except cannabis) at predose and during the course of the trial.

For subjects who are discontinued from treatment but continue to be monitored in the trial, all visits and procedures, as outlined in the trial flowchart, should be completed.

For subjects who are discontinued from treatment, all applicable discontinuation activities will be performed according to Section 7.1.4.1 – Withdrawal/Discontinuation, or if available, Protocol Clarification Letter.

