5.8.2 Withdrawal from the Trial

A subject must be withdrawn from the trial if the subject or subject's legally acceptable representative withdraws consent from the trial.

If a subject withdraws from the study, they will no longer receive treatment or be followed at scheduled protocol visits.

Specific details regarding procedures to be performed at the time of withdrawal from the trial including the procedures to be performed should a subject repeatedly fail to return for scheduled visits and/or if the study site is unable to contact the subject, as well as specific details regarding withdrawal from Future Biomedical Research are outlined in Section 7.1.4 – Other Procedures.

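### Sections 5.7.3.2 and 5.8.1 disagree on whether a subject with confirmed pregnancy leaves the trial; it matters only for a pregnancy confirmed after dosing and before the last visit

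*Combined protocol and SAP*

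**What the plan says.** Section 5.7.3.2 (Pregnancy Testing) schedules tests at pretrial, predose and the last trial visit. A positive result during the trial is repeated, and then: "If the pregnancy has been confirmed the subject must be discontinued from the trial immediately".

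Section 5.8.1 (Discontinuation of Treatment) treats the same event differently. Its list opens with "A subject must be discontinued from treatment but continue to be monitored in the trial for any of the following reasons", and one entry is "The subject has a confirmed positive serum pregnancy test". For subjects in that position, "all visits and procedures, as outlined in the trial flowchart, should be completed". The section separates the two statuses explicitly: "Discontinuation of treatment does not represent withdrawal from the trial".

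Section 5.8.2 adds: "A subject must be withdrawn from the trial if the subject or subject's legally acceptable representative withdraws consent from the trial". It names consent withdrawal and does not mention pregnancy, but it does not say that consent withdrawal is the only trigger.

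For anyone who discontinues, Section 7.1.4.1 lets the site ask her back for, or contact her about, a post-trial visit at about day 25. It also lets the investigator do the post-trial procedures at discontinuation or soon after. If the visit is earlier than day 25, an adverse-event call is due at day 25.

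**The concern.** Both sections use mandatory language for one event and reach opposite results on trial status. Neither refers to the other on this point, and nothing in the protocol sets an order of precedence. Section 5.7.3.2 is the pregnancy-specific text. Section 5.8.1 fits better with the reason given in the Summary of Changes for the 25-day follow-up, which is to cover the intracellular washout of MK-8504.

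What is at stake is in-person safety observation of a woman who has been exposed to the drug and is pregnant. A site that follows 5.7.3.2 may stop her scheduled visits. A site that follows 5.8.1 would keep them.

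**Working it through.** The plan gives no figure on this point, so the check compares the sections and adds a rough count.

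**1. When the conflict can arise.**
- *Predose.* Section 6.0, note c, assigns the randomization number only after the predose procedures. A woman found pregnant then has had no drug, so no post-dose monitoring is at issue.
- *After dosing, before the last visit.* No pregnancy test is scheduled. Confirmation needs an unscheduled test or a report, which Section 7.2.2 anticipates.
- *Last visit.* This is the 600 h/post-trial visit (25 days × 24 h = 600 h), so the scheduled visits are already complete or under way.

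**2. What is scheduled.** After the 24 h assessments, the Section 6.0 flow chart places physical examination, ECG, vital signs and safety laboratory tests at 168 h and 600 h/post-trial only.

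**3. What each section yields.**

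| Pregnancy confirmed | Under 5.8.1 | Under 5.7.3.2 with 7.1.4.1 |
|---|---|---|
| 24 h to 168 h | 168 h and 600 h sets both scheduled | At most one discretionary set, possibly early, plus a day-25 call if early |
| 168 h to 600 h | 600 h set scheduled | 600 h/post-trial set discretionary, possibly early, plus the call if early |
| At the 600 h test | Nothing outstanding | Nothing lost |

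If the discretionary set is done at once, the last in-person check precedes the 600 h visit by:
- confirmed at 24 h: (600 − 24)/24 = 24 days;
- confirmed at 168 h: (600 − 168)/24 = 18 days.

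**4. What continues under both.** Adverse events are reported through day 25 (7.2), as are serious adverse events (7.2.3.1). Reported pregnancies are followed to outcome (7.2.2).

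**5. How often.** Inputs are 18 to 24 subjects (Section 1.0), contraceptive failure at the 1% per year ceiling (5.7.3.1), and the assumption that every subject is a woman of childbearing potential, because the sex mix is not given.

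Expected conceptions = subjects × window/365 × 0.01

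- Low (18 subjects, 25 days after dosing): 18 × 25/365 × 0.01 = 0.012.
- High (24 subjects, 39 days, adding 14 days before dosing for a pregnancy too early for the predose test): 24 × 39/365 × 0.01 = 0.026.
- Conceived by 168 h (24 subjects, 14 + 7 = 21 days): 24 × 21/365 × 0.01 = 0.014.

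Only those confirmed by an unscheduled test or report before the last visit would meet the conflict.

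**6. Effect on the primary analysis.** The primary pharmacodynamic value is viral load at 168 h. Leaving before 168 h would cost a panel one of its 6 values, unless the subject is replaced under 5.9. Leaving later costs none. At the frequency in step 5 this is immaterial.

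**The case against.** The strongest reply has four parts.

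*The sections may not truly collide.* Section 5.8.1 says that "all subjects who discontinue trial treatment prior to completion of the treatment period will still continue to participate in the trial", and in this trial "each subject will be receiving assigned treatment for one day". After a single dose no treatment remains to discontinue, so it can be argued that 5.8.1 does not reach her. This shows that the reach of 5.8.1 is unclear. It does not remove the conflict, because the pregnancy entry in its list carries no such limit.

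*Both routes lead to 7.1.4.1.* Section 5.8.1 cites that section too, so the discretionary wording is not peculiar to 5.7.3.2. That is correct. However, 5.8.1 adds an explicit instruction to complete the flow-chart visits, and 5.7.3.2 has no counterpart.

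*A Protocol Clarification Letter could settle it.* Section 5.8.1 mentions this route. It could serve as a stopgap, but no such letter is part of the documents.

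*Little protection is lost.* This largely stands, given the reporting, call and outcome follow-up that continue.

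Some stronger readings are tempting and are not supported:
- A reader might infer that any post-dose pregnancy costs both the 168 h and 600 h visits. That holds only for confirmation before 168 h. The 600 h visit is itself the post-trial visit, so it becomes optional or moves earlier; no different visit replaces it.
- A reader might take the counts above as upper bounds. They are not. Section 5.7.3.1 defines abstinence as highly effective only from the day of dosing, the failure rate presumes consistent and correct use, and replacements can take enrolment above 24.
- A reader might regard the viral-load and resistance samples she would miss as purely research material. Section 2.1 ties possible emergent mutations to the choice of follow-on ART, so the documents do not support that.

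**Conclusion.** The inconsistency is real and the documents do not resolve it. Its consequence is narrow. For a dosed woman whose pregnancy is confirmed before 168 h, two scheduled safety sets become at most one discretionary set, plus a call if that set is early. Between 168 h and 600 h, one scheduled set becomes discretionary. At the 600 h test there is no loss.

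The expected number of conceptions is of the order of 0.01 to 0.03 in the whole trial. This is illustrative and rests on all subjects being women of childbearing potential and on 1% per year failure; fewer such women would lower it in proportion. There is no material effect on power or the primary analysis. This is a minor point, worth correcting because the rule as written in 5.7.3.2 points the wrong way for an exposed subject.

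**What to change.** Replace the sentence in Section 5.7.3.2 with:

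> If pregnancy is confirmed before dosing, the subject must not be dosed and does not continue in the trial. If it is confirmed after dosing, the subject continues, with her consent, to be monitored in the trial through the post-trial visit per Section 5.8.1 and the Section 6.0 flow chart, and the pregnancy is reported and followed per Section 7.2.2.

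Add to the pregnancy entry in Section 5.8.1 that it applies after dosing. The two sections then agree, and the doubt about 5.8.1's reach after a single dose is removed.

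The change should not touch ART timing. Section 2.1 already leaves ART initiation to the patient with the investigator or physician. If the sponsor wants to relax the 168 h wording for a pregnant subject, that belongs in Section 2.1; an override placed in 5.7.3.2 would create a new inconsistency.

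The cost is a short wording change in two sections at the next amendment, with no visits beyond the existing flow chart and no added patients.

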5.8 Subject Withdrawal/Discontinuation Criteria

5.8.1 Discontinuation of Treatment

Discontinuation of treatment does not represent withdrawal from the trial.

As certain data on clinical events beyond treatment discontinuation may be important to the study, they must be collected through the subject's last scheduled follow-up, even if the subject has discontinued treatment. Therefore, all subjects who discontinue trial treatment prior to completion of the treatment period will still continue to participate in the trial as specified in Section 6.0 - Trial Flow Chart and Section 7.1.4.1 – Withdrawal/Discontinuation, or if available, Protocol Clarification Letter.

Subjects may discontinue treatment at any time for any reason or be dropped from treatment at the discretion of the investigator should any untoward effect occur. In addition, a subject may be discontinued from treatment by the investigator or the Sponsor if treatment is inappropriate, the trial plan is violated, or for administrative and/or other safety reasons. Specific details regarding procedures to be performed at treatment discontinuation are provided in Section 7.1.4 – Other Procedures.

A subject must be discontinued from treatment but continue to be monitored in the trial for any of the following reasons:

- The subject or subject's legally acceptable representative requests to discontinue treatment.
- The subject has a medical condition or personal circumstance which, in the opinion of the investigator and/or Sponsor, placed the subject at unnecessary risk from continued administration of study drug.
- The subject has a confirmed positive serum pregnancy test.
- The subject has a positive urine drug screen (except cannabis) at predose and during the course of the trial.

For subjects who are discontinued from treatment but continue to be monitored in the trial, all visits and procedures, as outlined in the trial flowchart, should be completed.

For subjects who are discontinued from treatment, all applicable discontinuation activities will be performed according to Section 7.1.4.1 – Withdrawal/Discontinuation, or if available, Protocol Clarification Letter.

5.8.2 Withdrawal from the Trial

A subject must be withdrawn from the trial if the subject or subject's legally acceptable representative withdraws consent from the trial.

If a subject withdraws from the study, they will no longer receive treatment or be followed at scheduled protocol visits.

Specific details regarding procedures to be performed at the time of withdrawal from the trial including the procedures to be performed should a subject repeatedly fail to return for scheduled visits and/or if the study site is unable to contact the subject, as well as specific details regarding withdrawal from Future Biomedical Research are outlined in Section 7.1.4 – Other Procedures.

5.9 Subject Replacement Strategy

If a subject discontinues from trial treatment or withdraws from the trial, a replacement subject may be enrolled if deemed appropriate by the investigator and Sponsor. The replacement subject will generally receive the same treatment or treatment sequence (as appropriate) as the subject being replaced. The replacement subject will be assigned a unique treatment/randomization number. The trial site should contact the Sponsor for the replacement subject's treatment/randomization number.

The replacement subject may begin dosing at the subsequent dose level for that panel, based on investigator and Sponsor review and discussion.

5.10 Beginning and End of the Trial

The overall trial begins when the first subject signs the informed consent form. The overall trial ends when the last subject completes the last study-related phone-call or visit, withdraws from the trial or is lost to follow-up (i.e. the subject is unable to be contacted by the investigator).

A trial may be paused during review of newly available preclinical/clinical safety, pharmacokinetic, pharmacodynamic, efficacy or biologic data or other items of interest, prior to a final decision on continuation or termination of the trial. It may be necessary to keep the trial open for gathering/reviewing of additional supportive data to optimally complete the objective(s) of the trial. If necessary, the appropriate amendment(s) to the protocol and/or appropriate communication(s) will be generated. The overall trial end will then not be identified until the Sponsor has made the decision to end the trial following this review period. The Competent Authority(ies) and Institutional Review Board(s)/Independent Ethics Committee(s) [IRB(s)/IEC(s)] will be appraised of the maximum duration of the trial beyond the last subject out and the justification for keeping the trial open.

5.11 Clinical Criteria for Early Trial Termination

There are no pre-specified criteria for terminating the trial early.

A primary objective of this early Phase I trial is to identify the maximum safe and well-tolerated dose and/or dosing regimen that achieve pharmacokinetic, pharmacodynamic and/or biologic targets in humans based on preclinical or early clinical data. Therefore, it is possible that trial subjects may not receive all doses specified in the protocol if this objective is achieved at lesser dose levels in this trial. This would not be defined as early termination of the trial, but rather an earlier than anticipated achievement of the trial objective(s). If a finding (e.g., pharmacokinetic, pharmacodynamic, efficacy, biologic targets, etc.) from another preclinical or clinical trial using the trial treatment(s), comparator(s), drug(s) of the

same class, or methodology(ies) used in this trial, results in the trial(s) or program being stopped for non-safety reasons, this also does not meet the definition of early trial termination.

Early trial termination is defined as a permanent discontinuation of the trial due to unanticipated concerns of safety to the trial subjects arising from clinical or preclinical trials with the trial treatment(s), comparator(s), drug(s) of the same class or methodology(ies) used in this trial.

Enrollment of the trial will be halted in the following circumstances:

1. One subject reports a serious adverse event with a potential causal relationship to the study drug or two (2) subjects per panel report severe adverse events with a potential causal relationship to study drug.
2. Three (3) or more of the enrolled subjects experience the same adverse event requiring withdrawal from the study, or the same severe adverse event assessed as having a potential causal relationship to study drug.
3. Two (2) severe but not life threatening adverse experiences or severe clinically significant laboratory abnormalities that are similar in nature OR one (1) severe and life threatening adverse experience laboratory abnormality OR participant death thought to be potentially related to the investigational product.
4. Two (2) or more of the enrolled subjects experience confirmed QTcF > 500 ms or QTcF change from baseline >60ms in a given panel.

If the circumstances outlined in (1) or (2) or (3) above occur, enrollment and dosing will be halted and an internal safety review will be conducted, and the Sponsor will notify the competent authority where required of a halt to enrollment. Following the internal safety review, if the Sponsor deems it appropriate to restart enrollment and dosing, if required the Sponsor will submit a notification to the competent authority prior to restart. If approved, enrollment and dosing may restart at that time. If the circumstances outlined in (4) occur, enrollment and dosing will be halted and all available safety data will be reviewed to inform a decision about whether the study should continue. The safety of subjects will be assessed on an ongoing basis, and while conditions that could warrant early trial termination are not limited to those noted above, these criteria are meant to pre-specify circumstances under which the trial may be terminated early.

